8.6 PAIN ASSESSMENTS

Pain intensity of the VLU is to be assessed before any dressing changes or other wound manipulations at all screening visits, treatment visits, and at follow-up period visits.

Subject will be asked to rate his/her pain on a scale of 0 to 10 with 0 being “no pain” and 10 being the “worst pain possible”.

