9.1.1 GENERAL

Descriptive statistical methods will be used to summarize the data from this study with hypothesis testing performed for primary and secondary endpoints. These include number of subjects (n), mean, median, standard deviation, minimum, and maximum for continuous data, and frequencies and percentages for categorical data. All data collected during the study will be reported and analyzed.

Unless specified otherwise, all statistical testing will be two-sided and performed using a significance (alpha) level of 0.05.

All statistical analyses will be conducted using PASW 19.

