from the mean change in wound area and protease activity between baseline and 4 weeks after 4 weeks of CelluTome™ + SOC (**Group 1A**) versus 4 weeks of SOC (**Group 2A**) will be equal for both groups. Formally, $H_0: r_1 - r_2 = 0$; $H_1: r_1 - r_2 = D_1 \neq 0$, where r_1 is the Pearson correlation coefficient for subjects in **Group 1A** calculated from difference in mean wound area and difference in mean protease activity between baseline and 4 weeks, r_2 is the same specified metric for subjects **Group 2A**, D_1 is the difference ($r_1 - r_2$) assuming the alternative hypothesis, and the statistical test used is Steiger's Z test with the assumption that r will have the same sign for both groups.

H5: Correlation of wound area with protease activity at 8 weeks

The Pearson correlation coefficient (or Spearman's rho in the case of severe non-normality) calculated from the mean change in wound area and protease activity between baseline and 8 weeks after 8 weeks of CelluTome™ + SOC (**Group 1A**) versus 8 weeks of SOC (**Group 2B**) will be equal for both groups. Formally, $H_0: r_1 - r_2 = 0$; $H_1: r_1 - r_2 = D_1 \neq 0$, where r_1 is the Pearson correlation coefficient for subjects in **Group 1A** calculated from difference in mean wound area and difference in mean protease activity between baseline and 8 weeks, r_2 is the same specified metric for subjects in **Group 2B**, D_1 is the difference ($r_1 - r_2$) assuming the alternative hypothesis, and the statistical test used is Steiger's Z test with the assumption that r will have the same sign for both groups.

H6: Reduction in pain score at 12 weeks

The change in mean pain score between baseline and at 12 weeks after 12 weeks of CelluTome™ + SOC (**Group 1A**) versus 12 weeks of SOC (**Group 2B**) will be equal for both groups. Formally, $H_0: \mu_1 - \mu_2 = 0$; $H_1: \mu_1 - \mu_2 = D_1 \neq 0$, where μ_1 is the mean difference in pain score for subjects in **Group 1A** between baseline and 12 weeks, μ_2 is the same specified metric in **Group 2B**, D_1 is the difference ($\mu_1 - \mu_2$) assuming the alternative hypothesis, and the statistical test used is the paired t test if data are normal and the Mann-Whitney test on a non-paired basis if data are non-normal.

H7: Proportion of wounds healed at 12 weeks (Groups 2B versus 2C)

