9.7 STATISTICAL METHODS

MISSING DATA

Missing data may be the result of missed visits, subjects lost to follow-up or who have died, or data not available (e.g., smoking status).

Missing primary endpoint data within 12 weeks from start of study will not be imputed for ITT populations as these will constitute right-censored data in the time to heal analysis. The last visit for which data are available will constitute the start of censoring (healing outcome). For secondary endpoints within 12 weeks from start of study, the last observation carried forward (LOCF) principle will be used for ITT populations.

For adjusted analyses of primary and secondary endpoints, missing data for covariates used to adjust analyses may be imputed in separate models when the missing data for each covariate is $\leq 30\%$ and it can be reasonably demonstrated that the missing data for each covariate are MCAR.

FINAL ANALYSIS

Analysis can be started when database lock for the trial is initiated. In regard to statistical modeling, the initial list of independent variables will be examined for correlation between pairs. In the event that

correlation (however calculated) exceeds 0.7, a selection will be made between the 2 variables to avoid possible issues of co linearity and variance inflation.

The following analysis will be conducted:

1. Flow chart (subjects)
2. Overall trial statistics (enrollment dates, site numbers, numbers of subjects)
3. Demographics between groups at baseline (no statistical testing but identification of likely trial imbalances)
4. Count of subjects in each group
5. Primary endpoints within 6 and 12 weeks (time to heal; previously defined by groups) will be analyzed by Kaplan-Meier and log rank test (unadjusted); and then Cox regression to adjust for the following variables (with and without covariate imputation):

- Site
- Year enrolled (if trial lasts 2 years or more)
- Treatment group
- Initial area at randomization (cm²)
- Initial wound depth (cm)
- Age of wound at enrollment (days)
- Smoking status
- Prior VLU
- Pain score at randomization
- Patient age
- Gender
- Ethnicity/race
- VCS score
- Diabetes
- Patient on pain medications
- Smoking status
- BMI
- Infection episodes

6. Secondary endpoints will be analyzed as follows:

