- Reduction in pain score (baseline – Week 12) will be analyzed by paired t test if the dependent variable data are not grossly non-normal or the Mann-Whitney test if they are grossly non-normal (unadjusted).

To create the flow chart, the following numbers will be required for each group: eligible (n), screened (n), screen failure (n, with categorical reasons), randomized (n), completed 12 weeks study (n), withdrawals or lost to follow-up after randomization (n, with categorical reasons).

These variables are required for the final analysis:

- Site ID (alphanumeric)
- Patient ID (alphanumeric)
- Year enrolled (numeric; date, year only)
- Group assignment (nominal factor, [1A, 2A, 2B, 2C]; note: subjects in 2A can also have 2B or 2C assignments as well)
- Lost to follow up (binomial factor [1,0; 1 = yes]; estimated date lost to follow-up; associated patient ID; categorical reason for lost to follow-up)
- Death during study (binomial factor [1,0; 1 = yes]; estimated date when death occurred)
- Gender (nominal factor [1, 0; male = 1])
- Subject age at S1 (continuous variable with breakpoint at > 90 years if > 90)
- Ethnicity/race (multinomial factor)
- Smoking status at S1 (ordinal factor: [1, 2, 3; never, ever, current])
- Wound count (Poisson distribution variable; count of VLU at patient level at randomization)
- Index Ulcer location (multinomial factor)
- Prior VLU at S1 (binomial factor [1,0; 1 = yes])
- Wound age at S1 (continuous variable, days; S1)
- Pain score (continuous variable, 0-10, TV1 and 13)
- VCS score at S1 (continuous variable, 0-24)
- BMI at S1 (continuous variable)
- Diabetes at S1 (nominal factor [1, 0; yes = 1])
- Subject on pain medication at S1 (nominal factor [1, 0; yes = 1])
- Wound area (continuous variable, cm²; weekly, weeks TV1-13)
- Wound depth (continuous variable, cm; weekly, weeks TV1-13)
- Outcome healed at 12 weeks (binomial factor, [1,0; 1 = yes])
- Time to heal (continuous variable, 0-84, days after randomization for healed wounds)
- Initial wound healed within 12 weeks and confirmed closed about 2 weeks later (binomial, [1,0; 1 = yes])
- Ulcer recurrence by 12 weeks (binomial factor, [1,0; 1 = yes]; estimated days after randomization when event occurred)
- Infection episode (Poisson variable, weeks TV1-13)
- AE (Poisson distribution variable, count at patient level; date of onset)

CELLUTOME™ IN VENOUS LEG

- TEAE (Poisson distribution variable, count at patient level for each of 4 categories; date of onset)

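### The pain endpoint (H6) is planned as an unadjusted change score with an unsuitable paired test; regressing week-12 pain on group and TV1 pain would repair the test and gain precision from data already required

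*Combined protocol and SAP*

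**What the plan says.** - **Hypothesis.** H6 in section 9.2 concerns "The change in mean pain score between baseline and at 12 weeks after 12 weeks of CelluTome™ + SOC" (Group 1A) against 12 weeks of SOC (Group 2B). For normal data, "the statistical test used is the paired t test if data are normal". Only the Mann-Whitney alternative is described there as non-paired.
- **Final analysis.** Section 9.7, item 6: "Reduction in pain score (baseline – Week 12) will be analyzed by paired t test" if the data are not grossly non-normal, "or the Mann-Whitney test if they are grossly non-normal (unadjusted"). No adjusted pain model follows.
- **Data.** Section 8.6: "Subject will be asked to rate his/her pain on a scale of 0 to 10". Section 6.3 lists a pain assessment at TV1 before randomization. Section 9.7 requires "Pain score (continuous variable, 0-10, TV1 and 13") for the final analysis.
- **Use of baseline pain elsewhere.** "Pain score at randomization" is in the covariate lists for the Cox model (time to heal), the logistic model (proportion healed) and the repeated-measures GLM (protease).
- **Significance level.** Section 9.1.1: "all statistical testing will be two-sided and performed using a significance (alpha) level of 0.05".

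**The concern.** Two problems sit in the same sentence. First, a paired t test asks whether the mean within-subject change is zero. It does not test H6, which is a difference in mean change between two separate groups of patients.

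Second, the obvious repair, a two-sample t test on the change, fixes the coefficient on baseline pain at 1 instead of estimating it. Unless the true slope of week-12 pain on baseline pain is 1, this leaves avoidable noise in the treatment comparison. It also lets any baseline difference between groups feed into the result through regression to the mean. TV1 pain is already a required variable, so the loss is unnecessary. What is at stake is the width of the confidence interval and the power for a named secondary endpoint with formal testing.

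**Working it through.** **The plan's own figure.** The documents give no power, SD or correlation for pain. The only power figure is 86.1% for the logrank test on time to heal (section 9.3: 225 subjects, hazard ratio 1.74, control proportion healed 0.5, weekly dropout 0.033 and 0.0083). With exponential hazards these inputs give about 123 expected events and power of 85.0% (Freedman), 85.7% (Lakatos-type) and 86.7% (Schoenfeld). The figure reproduces, but it does not concern pain.

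**Direction of the gain.** Let s0 and s1 be the baseline and week-12 SDs and rho their correlation.

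- Var(change) = s0² + s1² − 2·rho·s0·s1
- Var(ANCOVA residual) = s1²·(1 − rho²)
- Difference = s0² − 2·rho·s0·s1 + rho²·s1² = (s0 − rho·s1)² ≥ 0

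So in large samples with comparable groups, ANCOVA is never less precise. The two are equal only when the slope b = rho·s1/s0 is 1.

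**Size if s0 = s1 (assumed).** The variance ratio is s²(1 − rho²) / [2s²(1 − rho)] = (1 + rho)/2.

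| Assumed rho | Variance ratio | Simulated | Reduction in SE |
|---|---|---|---|
| 0.3 | 0.65 | 0.64 | 1 − √0.65 = 19% |
| 0.5 | 0.75 | 0.74 | 1 − √0.75 = 13% |
| 0.7 | 0.85 | 0.86 | 1 − √0.85 = 8% |

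**Size if the variances differ (s0 = 1).**

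| rho | s1/s0 | Var(change) | Var(ANCOVA) | Ratio |
|---|---|---|---|---|
| 0.5 | 0.75 | 1 + 0.5625 − 0.75 = 0.8125 | 0.5625 × 0.75 = 0.4219 | 0.52 |
| 0.5 | 1.25 | 1 + 1.5625 − 1.25 = 1.3125 | 1.5625 × 0.75 = 1.1719 | 0.89 |
| 0.7 | 1.5 | 1 + 2.25 − 2.1 = 1.15 | 2.25 × 0.51 = 1.1475 | 0.998 |

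The gain therefore runs from large to about 0.2%, depending on values the documents do not give.

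**Illustration in power.** Section 5.1 anticipates 10% dropout in each arm and 30% of Group 2A switching. That leaves 112 × 0.9 ≈ 101 in 1A and 113 × (1 − 0.1 − 0.3) ≈ 68 in 2B. Take an assumed SD of 2.5 at both visits, a 1-point difference and two-sided alpha 0.05. Power is Φ(1/[SD_eff·√(1/101 + 1/68)] − 1.96), where SD_eff is 2.5·√(2(1 − rho)) for change and 2.5·√(1 − rho²) for ANCOVA.

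| rho | Change score | ANCOVA |
|---|---|---|
| 0.3 | 57.7% | 76.2% |
| 0.5 | 72.2% | 83.8% |
| 0.7 | 90.9% | 94.6% |

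**What adjustment does not do.** The two estimates differ by (1 − b) × (difference in mean baseline pain). Under randomization that baseline difference has expectation zero. Group 2B is what remains of 2A after subjects with area reduction below 40% at TV7 are moved to 2C (section 4; note C of the schedule). A baseline difference between 1A and 2B can therefore be systematic, and the two methods may then estimate different quantities. Neither undoes the selection.

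**The case against.** The strongest case on the other side is that, under randomization, a two-sample comparison of change is valid, so adjustment is only an efficiency preference. Pain is one of several secondary endpoints, and no error rate or sample size depends on the choice. That stands, and it limits the weight of the point without favouring the unadjusted analysis.

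Several stronger readings are tempting, and the documents do not support them:

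- **A fixed gain.** A reader might turn the ratios above into 54%, 33% or 18% more subjects (1/0.65, 1/0.75, 1/0.85) and treat that as the cost of the plan. Those figures need equal variances. Equality is doubtful here: about half the control ulcers are assumed to heal (section 9.3), closure counts as study completion (section 6.4), and missing secondary data are carried forward (section 9.7).
- **Over-correction at any correlation below 1.** This too needs equal variances. The general condition is b below 1.
- **Pain as the only endpoint without adjustment.** The other adjusted models are mostly conditional. Section 9.2 makes the Cox adjustment follow a significant result, although item 5 of section 9.7 lists it without that condition. The logistic model is optional. The GLM is optional after a significant difference. Adverse-event incidence has no adjusted version.
- **Adjustment as a cure for the 2B comparison.** It is not one, as shown above.

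It is also fair to object that the change-score comparator is not what H6 names for normal data. The precision figures describe the likely repair of the paired test, not the test as written.

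**Conclusion.** The point holds as a precision improvement at no data cost, together with the correction of a test that does not fit the hypothesis. The factual basis is in sections 9.2 and 9.7. The direction of the gain holds for any variances, given large samples and comparable groups. Its size is conditional: a variance ratio of 0.65 to 0.85 for rho of 0.3 to 0.7 if the two visits have equal variance, smaller gains (possibly near zero) if week-12 variance is well above baseline variance, and larger gains if it is below. The correlation, SDs and 1-point difference are assumptions.

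A reader might infer that the trial's power or sample size is misstated. It is not: pain has no power claim and the 86.1% for time to heal is unaffected. A reader might also take a regression on randomized arm as a drop-in replacement for H6. It would instead compare 1A with all of 2A, including subjects grafted after week 6, which is a different estimand from 1A versus 2B.

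**What to change.** In H6 (section 9.2) and item 6 of section 9.7:

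1. Replace the paired t test and Mann-Whitney test with a linear regression of TV13 pain on group, with TV1 pain and the wound-age randomization stratum (section 9.4) as covariates. Report the adjusted mean difference with a 95% CI. Specify a rank-based version for severely non-normal data.
2. State which comparison the model applies to. If it stays 1A versus 2B, say that adjustment does not remove the post-randomization selection of 2B. If it becomes 1A versus all of 2A as randomized, say that the estimand has changed.
3. Say how week-12 pain is obtained for subjects whose ulcer closes before TV13, since the carry-forward rule in section 9.7 would otherwise supply it.
4. Reconcile the schedule of events, which shows no pain assessment in the TV1 column, with sections 6.3 and 9.7, which both place one there.

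The cost is wording, settled before outcome data are examined. The model needs no new variable, visit or subject.

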The first hypothesis to be tested is that the proportion of wounds healed in **Group 2C** (12 weeks of SOC + 2 CelluTome™ applications) is no more than 15% lower than the proportion of wound healed in **Group 2B** (12 weeks of SOC). Noninferiority is established if the lower limit of the $(1 - 2\alpha) \times 100\%$ CI (confidence interval) for the difference (**Group 2C** – **Group 2B**) is above -15% where the equivalence margin, δ , is 15%. If non-inferiority is not established because the proportion of wounds healed in **Group 2C** is much higher than in **Group 2B**, the superiority hypothesis testing used in H2 will be utilized.

H8: Incidence of Adverse Events (AEs) (Groups 2B versus 2C)

The incidence of adverse events (AEs) by 12 weeks after 12 weeks of CelluTome™ + SOC (**Group 2C**; maximum of 2 CelluTome™ applications) versus 12 weeks of SOC (**Group 2B**) will be equal for both groups. Formally, $H_0: I_1 - I_2 = 0$; $H_A: I_1 - I_2 = D_1 \neq 0$, where I_1 is the incidence of AEs for **Group 2C** on a per subject basis, I_2 is same metric for **Group 2B**, D_1 is the difference ($I_1 - I_2$) assuming the alternative hypothesis, and statistical test used is the Mann-Whitney test.

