- SAE (Poisson distribution variable, count at patient level; date of onset; resolution; brief description)

ADJUSTMENT FOR FEWR

Adjustment to control for the family wise error rate (FEWR) (also known as multiplicity of testing) will use the Hochberg step-up procedure thus: Let $p_1 \geq p_2 \geq \dots \geq p_K$ be the ordered p-values and H_1, H_2, \dots, H_K be the corresponding null hypotheses. Reject H_k and all H_j for $j \leq k$ if $p_k \leq \alpha/k$. The adjusted p-values are $p_{adj,k} = \min \{p_1, 2p_2, \dots, kp_k\}$ for $k = 1, 2, \dots, K$.

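### The Hochberg rejection rule is written in the wrong direction: a small p-value would carry every larger one with it, and family-wise error control is lost

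*Combined protocol and SAP*

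**What the plan says.** Section 9.1.1 promises "hypothesis testing performed for primary and secondary endpoints" and sets the level: "all statistical testing will be two-sided and performed using a significance (alpha) level of 0.05". Section 9.2 then lists hypotheses H1 to H8, with H1 covering two time-to-heal comparisons (6 and 12 weeks).

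The multiplicity rule is in the last paragraph of section 9.7. It names the method: "Adjustment to control for the family wise error rate (FEWR) (also known as multiplicity of testing) will use the Hochberg step-up procedure thus". It then makes three statements.

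- Ordering: "Let $p_1 \geq p_2 \geq \dots \geq p_K$ be the ordered p-values"

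- Decision rule: "Reject H_k and all H_j for $j \leq k$ if $p_k \leq \alpha/k"

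- Adjusted p-values: "The adjusted p-values are $p_{adj,k} = \min \{p_1, 2p_2, \dots, kp_k\}$ for $k = 1, 2, \dots, K"

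The paragraph does not say which hypotheses form the family, how large K is, or whether the decision rule or the adjusted p-values govern.

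**The concern.** With p-values in descending order, index 1 is the largest and index K the smallest. The hypotheses with j ≤ k are therefore those with p-values equal to or larger than the k-th. A step-up procedure works the other way: once a p-value passes its threshold, that hypothesis and all those with equal or smaller p-values (j ≥ k) are rejected.

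Followed literally, the rule lets one endpoint with a p-value at or below alpha/K reject every other null in the family, however large the other p-values are. This paragraph is the trial's only multiplicity safeguard across the primary and secondary tests. The trial is also powered on the expectation of a real effect on time to heal, so a mixture of false and true nulls is the setting to plan for.

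**Working it through.** The documents state no family-wise error figure, so there is none to reproduce. The check compares the written rule with standard Hochberg and with the SAP's own adjusted p-values.

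**Inputs**
- Alpha 0.05, two-sided (section 9.1.1).
- Ordering, decision rule and adjusted p-value formula (section 9.7).
- Planned power 86.1% at 0.05 (section 9.3), used only to set a realistic size for one true effect.
- K is not stated. The range taken is K = 2 (the two tests in H1), 3, 7 (H2 to H8), 8 (H1 to H8 counted by label) and 9 (H1 counted as two tests).

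**The two rules**
- Written: if p_k ≤ alpha/k, reject H_j for all j ≤ k.
- Hochberg, same ordering: if p_k ≤ alpha/k, reject H_j for all j ≥ k.
- Adjusted p-value in both cases: the minimum of p_1, 2p_2, …, k·p_k.

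**Worked cases**

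| p-values | Thresholds met | Written rule rejects | Hochberg rejects | Adjusted p |
|---|---|---|---|---|
| 0.60, 0.01 | k = 2 (0.01 ≤ 0.025) | both | 0.01 only | 0.60, 0.02 |
| 0.90, 0.80, 0.70, 0.60, 0.50, 0.40, 0.30, 0.005 | k = 8 (0.005 ≤ 0.00625) | all eight | 0.005 only | 0.90 for the first seven; 8 × 0.005 = 0.04 for the last |
| 0.04, 0.03 | k = 1 (0.04 ≤ 0.05); k = 2 fails (0.03 > 0.025) | 0.04 but not 0.03 | both | 0.04, 0.04 |

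The third case shows that the written rule can also lose a legitimate rejection.

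**Consistency of the SAP's own formula.** On 5,000 random sets of p-values, the adjusted p-value formula agreed every time with a standard software implementation of Hochberg, and with the decisions of the j ≥ k rule.

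**Family-wise error, lower bound by hand.** Suppose one null is false and its test has 86.1% power at 0.05. Its mean z is 1.960 + 1.085 = 3.045. If its p-value is at or below alpha/K, then so is the smallest p-value, and the written rule rejects everything, including all true nulls. So family-wise error is at least Φ(3.045 − z for two-sided 0.05/K):
- K = 2: Φ(3.045 − 2.241) = 79%
- K = 8: Φ(3.045 − 2.734) = 62%
- K = 9: Φ(3.045 − 2.773) = 61%

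**Simulation** (40,000 runs per setting, independent two-sided z tests, error counted over the true nulls):

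| K | Written rule, one false null at 86.1% power | Hochberg (j ≥ k), same setting |
|---|---|---|
| 2 | 80% | 4.6% |
| 3 | 75% | 4.9% |
| 7 | 65% | 4.7% |
| 8 | 64% | 4.7% |
| 9 | 63% | 4.8% |

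If the one false null has a p-value close to zero, the written rule's error is 100% for every K. If all nulls are true, both rules give 4.7% to 5.1%, because both make at least one rejection under the same condition.

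**The case against.** The strongest reply is that this is a slip, and that most of the paragraph is right. The method is named correctly and the adjusted p-values are correct. An analyst who runs standard Hochberg software or reports those adjusted values keeps control. Only someone who follows the decision sentence and ignores its neighbours would incur the 80% or 63%, and the oddity of rejecting 0.04 but not 0.03 would probably be noticed. All of this is fair. It makes the harm less likely, but the explicit rejection instruction still contradicts the formula after it, and nothing in the SAP says which prevails.

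The magnitudes also depend on the scenario. The small p-value must first meet its own threshold (0.05/9 ≈ 0.0056 for the smallest of nine). K is assumed. The tests would not be independent here: the 6- and 12-week comparisons share Group 1A, and H2 uses the same healing outcome and groups as the 12-week test in H1. These points stand as limits on the exact percentages. The 100% result for a p-value near zero depends neither on K nor on independence.

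Rejecting every null would also not amount to a favourable claim on every endpoint. H3 and H8 compare adverse event incidence, H4 and H5 compare correlations, and H7 is first decided by a confidence limit rather than an ordinary p-value. That too is right. It narrows what could be claimed without making the rule valid.

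Finally, everything turns on one inequality sign, which is worth confirming on the original PDF page. The alpha/k thresholds and the adjusted p-value formula both fit the descending order, so the fault lies in that sign alone.

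**Conclusion.** The concern holds. The decision rule in section 9.7 is wrong as written and contradicts the adjusted p-values in the sentence after it; no other section corrects it. Where at least one null is false, the written rule does not control family-wise error. With one real effect at the planned power and the remaining nulls true, the error is 63% to 80% over K = 9 down to K = 2, assuming independent tests, against about 5% for the correct rule. Where all nulls are true there is no inflation. The reversed direction itself rests on none of these assumptions. It must be fixed, because a prespecified plan should not permit two different sets of conclusions from the same data.

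**What to change.** In section 9.7, change the decision rule so that, in the descending ordering, meeting alpha/k rejects H_k and all H_j with j ≥ k. Keep the adjusted p-value formula, and state that claims are based on adjusted p-values of at most 0.05. With this change, simulated family-wise error is 4.6% to 5.1% in every setting examined, and the decisions match the SAP's own adjusted p-values.

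The same edit should list which of H1 to H8 belong to the family, say whether H1 counts as one test or two, and say how H7's confidence-limit test is handled. Without this K is undefined, and even the corrected rule cannot be applied in a unique way.

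The cost is one symbol and two or three sentences, with no effect on sample size, data collection or conduct. It should be done before database lock; a correction made once results are known would look data-driven.
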